The patients will be randomized with 1:1 ratio of intervention and control groups, in blinded blocks of 5, randomly assigned by software used on www.randomizer.org to create 60 study patients and 60 control patients. Envelopes will be used to assign the patients in blocks of 5. Therefore in the first group is to be a control group, the first 5 patients will be controls, then the next group of 5 will be randomly assigned to control or intervention group based on a randomized protocol listed on a study envelope. Overall the blocks of 5 will create even groups of control and intervention patients overall to reach the 120 patient goal. One member of the study team, not involved in the surgical procedure and post-operative pain evaluation will be designated unblended and will communicate with the anesthesiology team pre-operatively to determine whether the patient is to receive methadone or not. The anesthesia team will be responsible for allocation and administration of the methadone, in addition to the standard fentanyl and ketamine, from the Montefiore pharmacy which is already available for intra-operative use as an alternate narcotic regimen. Post-operatively, blinded team members will collect pain data, as well as time to ambulation and discharge data. The pain measures will be patient derived, and time to event data will be part of the patient's chart.

Describe what safety outcomes will be monitored

Safety outcomes to be measured as stated in the adverse events section of this protocol include risks of using any opioid narcotic, which include overdose leading to respiratory depression, dependence and QTc prolongation. Psychological risks include obtunded, lethargic state or altered mental status due to long half-life and opioid effects post-operatively and any resultant mental distress, especially in opioid-naïve patients

Include a data safety monitoring plan

A data safety monitoring plan is included in section 7, under the subheading "Describe methods for interim analyses or early stopping, if applicable"

➤ For Observational studies

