case and will administer a 0.2 mg/kg single-dose administration of methadone on incision (not to exceed 20 mg, as used in the literature) with a ketamine infusion of 4 µg/kg/min and a remifentanil infusion starting at 0.1 µg/kg/min and titrating to effect or sufentanil infusion starting with a dose of 0.3 µg/kg/hr and titrating to effect. These standard doses have been well documented and studied in the literature as demonstrated above and will be overseen and have been approved by board certified anesthesiologist. For lengthier procedures, there will not be re-dosing of narcotics toward the end of the procedure. The operative procedure will not be altered in any way for the purposes of this study, and is beyond the scope of this protocol, yet can be detailed as requested. The patient will be taken to the recovery room postoperative and will be put on a standard post-operative morphine PCA as used in our department at a rate of 1mg per 6 minute lock-out period. This standard dose and therapy has been used in nearly all postoperative lumbar fusion patients to date. Patient's narcotic usage and pain rating will be recorded at the intervals listed above and when stable from a cardiovascular standpoint, will be transition to the neurosurgery floor. Once able to bare weight, the patient will be encouraged to work with physical and occupational therapy as per standard post-operative protocol. One the patient uses the PCA at a rate of less that once an hour, and can be managed with oral pain medications, the PCA will be removed. The remainder of their post-operative care will be according to the standard departmental protocol, and when milestones such as ambulation, voiding, and pain control are met, they will be discharged either to home, an acute care facility, or a subacute rehabilitation center. Per standard of care, the patients will return to the clinic at 2 weeks and 3 months as part of their routine clinical care. Any adverse events/reactions will be recorded and managed as normally they would be, and naloxone will be available for suspicion of narcotic overdose. Patient assigned to the control group will be monitored in the manner post-operatively, as is the standard of care for all of our patients.

Define the outcome measures pertaining to each aim.

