The sample size was determined using the Gottschalk study listed in the reference section which used methadone vs. sufentanil in 29 patients undergoing lumbar fusion surgery and the measures for pain level and total narcotic usage at 48 hours to determine an 'n' for the total study population, using a power of 0.80. The details of the calculations is listed in the data analysis section (7a) below and calculated with the suggestion of the statistician on the IRB. The assumptions with which the outcomes are hypothesized are the result of previously published data using similar populations. Two sample t-tests are appropriate to determine statistical significance between mean pain scores between different patients in the control and study groups for each individual time point as there will be no censoring of the study data. Ranked T-test may also be used if outliers are present, however patients with unusual post-operative courses may be excluded if their reason for prolonged hospitalization is unrelated to immediate post-operative pain

control. The large sample size plans to take into account possible outliers that may not be included in final analysis, despite their mention in study write-up to determine why their post-operative hospitalization was prolonged. Additionally, data about patients' mean time to ambulation, mean time to discharge, and mean overall narcotic usage will be measured between the control and study populations. Data analysis will be performed with the assistance of the biostatistician listed as a member of the study team, [name], from the Albert Einstein College of Medicine, Division of Biostatistics. Thus, a sample of 60 completed methadone patients will be evaluated against 60 randomized, standard narcotic regimen controls. The mean data for control patients' pain ratings, narcotic usage, time to ambulation, and time to discharge will be obtained, the statistical deviation of this data will be measured and compared to subject data in all facets.

• Take into account anticipated drop-out or loss-to-follow up rate.

We intend to screen 200 patients to have 60 in each arm ultimately included in the study. Since the intervention is a single intra-operative occurrence, that when completed patients cannot reverse, we do not anticipate any drop-out. A two week follow-up visit is a required standard of care for all post-operative patients, without patient loss to follow-up historically. The study is completed at this point.

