Two sample T-tests will be performed to evaluate continuous variables such a total morphine dose, pain level per VAS, time to first morphine dose, time to ambulation, and time to discharge. The assistance of a statistician, [name], from the Albert Einstein College of Medicine, Division of Biostatistics will be used for statistical analyses performed in this study. Wilcoxon Rank Sum Test will be used if outliers are noted in the study population, detected as more than 5 MAD from the median, and a concern presents that single patients may skew the data. Additionally, review of these patients who are outliers may also necessitate their exclusion from this work if they provide data that will significantly modify the mean of the remaining patients. This can be accounted for in the goal of 60 patients to be accrued in each arm of the study. A thorough explanation and review will performed on any such patients in any form of write up of this work.

At least one study hypothesis (or a statement that the study is hypothesis-generating or a feasibility study):

The use of single dose intraoperative methadone will decrease total narcotic usage, time to ambulation, mean pain rating at 24 and 48 hours and will decrease number of days of hospitalization compared to sufentanil (current standard of care) controls.

• A statement regarding specifically what data are to be used to test the hypothesis (or to generate the hypotheses)

We will obtain data of total narcotic usage, days until patients ambulate with physical therapy, pain ratings at 24 and 48 hours, and days to discharge, all obtained from the patient's medical record.

- o The statistical method(s) to be used to test the hypothesis with that data
 Two-sample T-test will be used with the assistance of an Albert Einstein statistician, [name], to analyze
 the above data and determine if there is statistical significance between the two groups, in addition to the
 stipulations outlined above to address outlier patients.
- A power analysis to determine the sample size (even for pilot studies)

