 We proposed to recruit 60 patients to undergo the new treatment and another 60 as controls. This gives us greater than 80% (95%) power to detect an improvement of 0.56 (0.74) within-group standard deviation at statistical significance level 0.05 as had been calculated to be 51 patients per group. Using 60 patients will ensure the usability of our data to detect differences of this effect sizes between groups. From our preliminary data, the standard deviation of time to discharge is 6.7 days, therefore, our sample size is able to detect an average reduction of 3.8 days (5.0 days) in time to discharge with 80% (95%) power.

Describe methods for interim analyses or early stopping, if applicable A data safety monitoring committee will be organized for the purposes of data evaluation in this study.

The members of the committee will include [name], neurosurgeon in the Department of Neurosurgery who performs spinal surgeries yet is not involved in the implementation of this project, and [name], statistician in the Department of Epidemiology and Population Health who is not involved in this protocol. After 20 patients complete the study (approximately 10 patients in each arm), interim analyses will be performed to compare pain ratings, narcotic usage, time to ambulation, and time to discharge to control patients, and the data safety monitoring committee will be asked to review all results and advise the study personnel as well as the IRB about study continuation. If there a significant increase in any of these measured values beyond a single standard deviation of the mean, the data safety monitoring committee and the IRB will come to a decision regarding continuation of the study. Assuming the outcome follows a normal distribution, with 10 patients in each arm, and under the null hypothesis that there is no difference between two groups, the chance of observing a difference greater than or equal to one standard deviation between two groups is about 1/100000. With four measures considered here, the overall Type I error will be no greater than 5/100000. Therefore, the loss of power from the

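### Respiratory depression and altered mental state are named safety outcomes, but no between-arm summary of any adverse event is specified, and the removal rules could take harmed patients out of the analysed data

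*Combined protocol and SAP*

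**What the plan says.** **Safety outcomes.** Section 2, under the safety outcomes to be monitored, states: "Safety outcomes to be measured as stated in the adverse events section of this protocol include risks of using any opioid narcotic". It then names overdose with respiratory depression, dependence, QTc prolongation, and an obtunded, lethargic or altered mental state. Under planned interventions it adds: "Any adverse events/reactions will be recorded and managed as normally they would be, and naloxone will be available for suspicion of narcotic overdose". Section 6 has nurses watch for respiratory depression after extubation, and section 3 says the medical record holds all data the study needs. Neither the primary nor the secondary outcome list contains an adverse event.

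**Planned comparisons.** Section 7(a) states: "Two sample T-tests will be performed to evaluate continuous variables such a total morphine dose, pain level per VAS, time to first morphine dose", followed by time to ambulation and time to discharge. The Wilcoxon rank sum test is the alternative if there are outliers. Section 3 describes the same kind of comparison. The interim analysis, after 20 patients, compares pain ratings, narcotic usage, time to ambulation and time to discharge.

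**Other uses of adverse events.** Recruitment is held if methadone contributes more adverse events than normal (more than 2 patients). An in-hospital death gets a cause analysis. The monitoring committee reviews all interim results.

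**Removal of patients.** Section 3 says "patients with unusual post-operative courses may be excluded if their reason for prolonged hospitalization is unrelated to immediate post-operative pain" control. Section 7(a) allows outlying patients to be excluded if they would noticeably shift the mean. The interim-analysis text keeps a death attributed to surgery out of the analysis and reports it separately.

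**The concern.** The plan commits to measuring certain harms and then does not say how they will be summarised by arm. Followed as written, the final report would contain tests on pain, opioid use and recovery, plus narratives for unusual patients. It need not contain an estimate of how often patients in each arm had respiratory depression or a clouded mental state.

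A missing adverse-event table alone would be a gap in detail. The removal rules make it more serious, because each is triggered by something that happens after treatment: a long stay, an extreme value or a death. A serious opioid-related event can cause any of these. Unless safety has its own analysis set, patients who were harmed could leave the data, possibly at different rates in the two arms, and a case narrative cannot restore a denominator.

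Section 6 justifies the risk partly by saying that the alternative opioid carries the same medical risks. The trial randomises 120 patients, yet no estimate bearing on that statement is planned.

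**Working it through.** **1. The plan's own figure.** The only sample-size calculation is for a continuous efficacy outcome: "greater than 80% (95%) power to detect an improvement of 0.56 (0.74) within-group standard deviation". The plan derives 51 per group from this, using a 0.05 level. With n = 2(z₀.₉₇₅ + z₀.₈₀)²/d² and d = 0.56, this is 2 × (1.960 + 0.842)²/0.56² = 15.70/0.3136 = 50.1, or 51 per group, which reproduces the plan. At 60 per group the power is 87% at 0.56 SD and 98% at 0.74 SD (normal approximation). With an SD of 6.7 days, 0.56 × 6.7 = 3.75 and 0.74 × 6.7 = 4.96 days, matching the stated 3.8 and 5.0. The efficacy sizing is sound. No figure is given for any safety comparison.

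**2. Is each place where adverse events could be analysed a comparison of arms?**

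| Place in the protocol | What it covers | Compares arms on an adverse event? |
|---|---|---|
| Section 2, outcomes | opioid use, ambulation, stay, disposition, questionnaires, pain, dexamethasone need, fusion | No |
| Sections 3 and 7(a), tests | opioid dose and timing, pain, ambulation, discharge | No |
| Section 7, interim comparison | pain, opioid use, ambulation, discharge | No |
| Section 7, hold on more than 2 patients | events attributed to methadone | No control-arm count is used and 'normal' is undefined |
| Section 7, death review | cause of each death | No |
| Section 7, committee review | all results, after 20 patients | No method or table is specified |

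**3. Could the hold rule stand in for a comparison?** Let X be the number of methadone patients with an event among 60, with the true rate equal to control's. P(X ≥ 3) = 1 − P(X ≤ 2) under Binomial(60, p).

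| Rate p, same in both arms | P(X ≥ 3) |
|---|---|
| 2% | 12% |
| 4% | 43% |
| 6% | 71% |
| 10% | 95% |

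The count can pass 2 with no excess over control, so it does not measure a difference between arms.

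**4. What would a by-arm estimate show?** The only respiratory event rates in the documents are in section 1, from a caesarean series: 1/25 = 4% with methadone and 3/50 = 6% in controls. They are used here as illustrative assumptions. At 60 per arm they give 0.04 × 60 = 2.4 and 0.06 × 60 = 3.6 events, so roughly 2 to 4 per arm.

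The Newcombe interval for d = p₁ − p₂ (methadone minus control) combines the Wilson limits (l, u) of each arm:
lower = d − √[(p₁ − l₁)² + (u₂ − p₂)²]; upper = d + √[(u₁ − p₁)² + (p₂ − l₂)²].

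- Wilson limits: 2/60 gives 0.0092 to 0.1136; 4/60 gives 0.0262 to 0.1593.
- 2 vs 4: d = −0.0333; lower = −0.0333 − √(0.0241² + 0.0926²) = −0.129; upper = −0.0333 + √(0.0803² + 0.0404²) = +0.057.
- 4 vs 4: d = 0; the limits are ±√(0.0926² + 0.0404²) = ±0.101.
- 0/60 in one arm: the two-sided exact 95% upper limit is 1 − 0.025^(1/60) = 6.0%.

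**5. Would a formal test help?** Fisher's exact test, two-sided 0.05, 60 per arm, by full enumeration:

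| Control vs methadone rate | Power |
|---|---|
| 4% vs 8% | 6.0% |
| 6% vs 12% | 11.8% |
| 4% vs 12% | 23.0% |
| 6% vs 18% | 42.2% |

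A non-significant result would therefore be expected even if the true rate had doubled. An interval is the useful output.

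**The case against.** **The list of tests is open-ended and the committee reviews all results.** The t-test list is introduced as examples, so the analysts may well tabulate adverse events. This stands: the supportable statement is that no comparison is specified. A reader might infer that the arms will never be compared on harm, but the documents do not say so. Against that, the list is of continuous variables, which yes/no events do not fit, and a review after 20 patients is not a final analysis.

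**Adverse events are used.** The hold rule, the death review and the required reporting of deaths are real safeguards, so it would be wrong to say the plan ignores harm. None of them gives an estimate by arm.

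**The gap is general.** No method is given for disposition, dexamethasone need or fusion either. This stands, and it rules out reading the omission as selective.

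**Over-sedation is arguably part of pain control.** If so, the prolonged-stay rule would keep such a patient in. This also stands: the wording can be read either way, exclusion is optional, and excluded patients must be described in the write-up. The possibility is enough to justify a protected safety set; it does not demonstrate bias.

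**The referenced adverse events section.** No section has that title, but section 6 carries nearly the same risk text, so this may only be a mislabelled cross-reference. Section 6 gives no analysis.

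**The trial is too small for safety.** True for a test. It supports reporting an interval.

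**Conclusion.** The concern holds in this form: the plan names safety outcomes and says adverse events will be recorded, but specifies no between-arm summary or comparison of any of them, and three removal rules could take harmed patients out of the analysed data. It should be corrected. It does not undermine the efficacy sizing.

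The intervals in the working show what remains open: at 2 vs 4 events a methadone excess of nearly 6 points is still compatible with the data, and at 4 vs 4 an excess of about 10 points. These figures assume 60 analysed patients per arm and event rates borrowed from caesarean patients. The present trial has a different operation and excludes sleep apnoea and home oxygen, so its rates may differ. Four methadone-arm events also assume that the trial continued after any hold. That the events can be recovered from the chart is an inference from sections 2, 3 and 6, since no definition or time window is given.

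Two stronger readings should be avoided. A reader might infer that the risk justification rests on the background statement that methadone adds no adverse events. That sentence summarises earlier literature; the justification in section 6 is that the alternative opioid carries the same risks and that less opioid is expected afterwards. A reader might also infer that the plan commits to claiming equal safety. Its stated hypothesis makes no safety claim.

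**What to change.** Add to section 7(a):

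- For respiratory depression, naloxone administration, and obtunded or altered mental state, report the number and percentage of patients per arm and the risk difference with a 95% confidence interval (for example Newcombe). The study team fixes the chart definition and time window of each event before unblinding.
- Tabulate any recorded QTc prolongation or dependence by arm.
- The safety set is every patient who received study anaesthesia, grouped by drug received, with no removal for outlying values, prolonged stay or death.
- A non-significant difference will not be reported as evidence of equal safety.

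The blinded team members who already collect post-operative data can abstract these fields. Correct the cross-reference to the adverse events section at the same time.

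The cost is one paragraph, the event definitions, a few yes/no fields in the chart abstraction and one table. No new visits, tests or patients are needed. The downside is that the intervals will be wide, so the safety statement in the report must be modest. The change concerns analysis and reporting only and leaves clinical management and the hold rule as they are.

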Age <21 or >80, renal failure requiring dialysis or serum creatinine greater than 2.0, significant hepatic dysfunction (liver function tests greater than twice the upper limit), hepatic cirrhosis, pulmonary disease requiring home oxygen therapy, obstructive sleep apnea, severe heart disease, allergy to methadone, morphine, ketamine or fentanyl, **recent or distant history of opioid abuse,** opioid use equal to or greater that the equivalent of 10mg morphine per day, poorly managed psychiatric illness, a known history of alcohol abuse, morbid **obesity (for the purposes of this study body mass index > 50 kg/m2),** treatment with other NMDA receptor antagonists, HIV-1 protease inhibitors, erythromycin or ketoconazole, prolonged QTc on pre-operative EKG, and the refusal or inability to sign the consent form to agree to participate in this study.

State primary and secondary outcome(s)

The primary outcomes for the study include total narcotic dose post-operative, frequency of narcotic use, the time to first ambulation after surgery with PT, length of stay, disposition (i.e. level of rehabilitative care), and improvement on clinical questionnaires in the intervention group as compared to the control group. Secondary outcomes include better subjective pain control, need for post-operative course of

dexamethasone for post-operative/post-fusion radiculopathy or neurapraxia/neuropathy and fusion at 3-6 months.

> For Randomized clinical trials

• Indicate whether a parallel or crossover study, and the number of treatment groups
The study will take the form of a parallel, 2 arm analysis of a methadone treatment group or a
group receiving the current standard of care without intra-operative methadone administration.

• Describe randomization and blinding procedures

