• Describe predictors of interest along with potential confounders and effect modifiers Predictors of interest include drug abuse history and/or behavior, as well as anticipated benefit from history of medication usage in the literature. Potential confounders include previous narcotic use history, narcotic tolerance/dependence in patients not otherwise excluded during recruitment, variable pain thresholds and tolerance amongst different patients, duration and complexity of surgeries, as well as variable renal clearance. Many of these are also effect modifiers.

• Describe matching criteria, if applicable

Matching criteria will not be used at this study will be structured as a randomized control trial.

• Describe duration of follow-up, and timing of data collection

Post-operative imaging will be reviewed to determine successful decompression and instrumentation. Data collection will be done during patient's hospital stay. Patients will be asked about their post-operative pain at 4 hour intervals, and data regarding their overall narcotic usage and their time to ambulation will be recorded from the medical record. Follow-up will then consist of: 1 week for phone call by spine NP, 2 week evaluation as is standard for all post-operative patients.

• Describe the planned interventions and their timing.

A study participant will be randomized ahead of time to be administered methadone or the current standard of care in blocks of 5 blinded to clinical personnel. If the patient is assigned to the methadone group, the anesthesiology team will be given this information and the anesthesiologist assigned to the Revised 4/17/13, 6/23/15

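### The primary opioid total has no time window, drug list or common unit, so it can fall without any fall in opioid need

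*Combined protocol and SAP*

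**What the plan says.** The opioid outcome is described in several places:

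- Section 2, outcomes: "The primary outcomes for the study include total narcotic dose post-operative, frequency of narcotic use". Length of stay is in the same list of primary outcomes.
- Section 2, follow-up and timing: "Data collection will be done during patient's hospital stay", and "data regarding their overall narcotic usage and their time to ambulation will be recorded from the medical record". A one-week phone call and a two-week visit follow, with no mention of recording opioid use after discharge.
- Section 2, planned interventions: patients start on a morphine PCA. Once they use it less than once an hour "and can be managed with oral pain medications, the PCA will be removed". The oral drugs are not named.
- Section 3, sample size: a published 29-patient trial supplied "the measures for pain level and total narcotic usage at 48 hours to determine an 'n' for the total study population".
- Section 7a, methods: two-sample t-tests for "continuous variables such a total morphine dose, pain level per VAS" and other variables.
- Section 7a, data for the hypothesis: "We will obtain data of total narcotic usage, days until patients ambulate with physical therapy, pain ratings at 24 and 48 hours". The 24 and 48 hours belong to the pain ratings.

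Morphine equivalents appear only in the eligibility rules, never in the definition of the outcome.

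**The concern.** An outcome compared between arms should be counted over the same period and in the same currency for every patient. Here the period is left to the chart, so it ends at an event that treatment may move.

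There are two readings, and the plan does not choose between them:

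- **All opioids counted.** The total ends at discharge. Sections 2 and 7 hypothesise earlier discharge with methadone. A patient who leaves sooner has fewer days counted, even if daily need is unchanged.
- **Morphine only.** The count largely ends when the PCA comes off. That time depends on how much opioid the patient is using, so it depends on treatment. A non-morphine oral opioid taken afterwards is not counted.

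At stake is what a significant result would mean. The trial could report lower opioid use when it has shown a shorter stay or an earlier switch of drug. The open definition also leaves the choice of total to be made after the data are seen.

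**Working it through.** **1. The plan's own figure.** Inputs from section 7a: 0.56 SD, 80% power, significance level 0.05 (two-sided reproduces the figure). n per group = 2(1.960 + 0.842)² / 0.56² = 15.70 / 0.3136 = 50.1, rounded up to 51, as stated. With 60 per arm, power at 0.56 SD is about 86-87%. Also 0.56 × 6.7 = 3.75 days (stated as 3.8) and 0.74 × 6.7 = 4.96 days (stated as 5.0). The concern does not rest on an arithmetic error. The only SD given in natural units is for time to discharge. There is no mean or SD for opioid dose and no mean stay.

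**2. All-opioid reading.** Let U be use in the first 48 hours, r the daily use after that, and L the stay in days. For stays of at least two days, the in-hospital total is U + r × (L − 2). If U and r have the same distribution in both arms, with r unrelated to stay, the difference in mean totals is mean r × the difference in mean stay. For the latter take 3.8 days, which section 7a gives as the difference detectable with 80% power. The daily dose is an assumption:

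- r = 0: 0 mg
- r = 10 mg/day: 3.8 × 10 = 38 mg
- r = 30 mg/day: 3.8 × 30 = 114 mg

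A partial anchor is in section 2: 1 mg per demand at under one demand an hour is below 24 mg/day when the PCA is removed. If the assumed range is in intravenous units, its top end lies above that.

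**3. Morphine-only reading.** If oral non-morphine opioid runs at the same assumed 10-30 mg/day, each day earlier off the PCA leaves 10-30 mg uncounted. If the oral drug is morphine or not an opioid, nothing is hidden. Steps 2 and 3 are alternatives and must not be added.

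**4. Effect on a t-test, by simulation.** 60 per arm, two-sided 0.05, 2,000 trials per setting. Assumptions not in the documents: control mean stay 7 or 10 days, everyone in hospital at least 48 hours, gamma-distributed stay beyond that, lognormal daily use (log SD 0.5), and use after 48 hours constant at 10%, 25% or 50% of the early daily rate. The SD of stay is 6.7 days (section 7a).

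*Same daily use in both arms, methadone stay 3.8 days shorter on average* (stay beyond 48 hours scaled down proportionally). Share of trials significant:

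| Late use | 48-hour total | Open total, 7-day stay | Open total, 10-day stay |
|---|---|---|---|
| 0% | 4-5% | 4-5% | 4% |
| 10% | 5% | 33% | 28% |
| 25% | 5% | 78% | 59% |
| 50% | 5-6% | 95% | 77% |

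In the control arm the open total correlates 0.40 to 0.75 with stay when late use is 10-50%.

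*True effect of 0.56 SD on the first 48 hours only, equal stays.* Power is 84-87% with the 48-hour total. With the open total and 10-50% late use it is 59% down to 12% (7-day stay) or 50% down to 11% (10-day stay).

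**The case against.** The best defence is that an in-hospital total is implied by the data-collection text and is a legitimate outcome. If methadone shortens stay, opioid given in hospital really does fall. That stands: it would be wrong to call 38-114 mg a false reduction. It would mislead only as evidence of lower need.

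Four stronger readings are tempting but not supported:

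- *The plan analyses morphine alone.* Section 7a names morphine in an illustrative list. The same section states the hypothesis and the data to be obtained in terms of total narcotic usage, and applies the t-test to those data. The labels are inconsistent, but a morphine-only analysis is not established.
- *Section 3 gives a competing 48-hour definition.* It describes the measures of the earlier trial used for sizing. By the same token it cannot be read as supplying this trial's window.
- *Both mechanisms act together.* If all opioids count, removing the PCA hides nothing. If only morphine counts, later hospital days add little.
- *Variation in stay is noise unrelated to analgesia.* Section 2 makes pain control a discharge milestone, so stay partly reflects analgesia.

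The plan also allows exclusion of long stays unrelated to pain (section 3) and a Wilcoxon test when outliers appear (section 7a). These may limit the influence of extreme stays. They are applied after randomisation, partly at discretion, and do not remove a difference in stay between arms.

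Finally, nothing in the documents compels 48 hours. Section 1 reports analgesia for up to 108 hours after one dose.

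**Conclusion.** The concern holds in this form: the primary opioid outcome lacks a window, a drug list and a unit. Whichever reading is adopted, its value depends on an event that treatment may move. A lower total would then not show lower opioid need, and if methadone acts as hypothesised the distortion favours it.

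Confidence is high on the missing definition and on the direction. The size is not known. The milligram figures assume a constant late dose that the documents do not give, and 3.8 days is a detectable difference, not an expected one. The simulated percentages show that the problem can be large with modest late use and vanishes when no opioid is counted after 48 hours. They are not estimates of this trial's error rate. The sample size of 51 per group in SD units is unaffected.

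**What to change.** Use one definition in sections 2, 3 and 7: cumulative opioid from arrival in the recovery room over one fixed window, all drugs and routes, in morphine equivalents from one conversion table fixed in advance. A 48-hour window matches the measure used for sizing. Report whole-stay totals and mg per day as descriptive only.

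State in advance how discharge before the window ends is handled, because the chart stops there. Counting unobserved hours as zero would bring the dependence on stay back. The one-week phone call already planned is a possible source for the missing hours, though it relies on recall.

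The cost is wording in three sections and a conversion table. Section 3 says that the data needed are in the medical record, so no new in-hospital collection should be required, provided that doses are charted with times. Patient care is unchanged. The price is that opioid use after the window is not in the primary figure. A longer window would capture more of it, but more patients would be discharged before it ends.
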